In the context of finite NHS resources, there are cost implications to consider. Cost of surgery ranges from £2 897 to £5 593 depending on complexity with a further £115 to £204 for a course of post-operative rehabilitation with a NHS physiotherapist. The cost of post-operative rehabilitation is similar to the cost of out-patient NHS physiotherapist-led exercise (up to six sessions). In the UK, post-operative rehabilitation typically consists of immobilisation in a sling for up to six weeks followed by an exercise programme to regain movement, strength and function over a three to six-month period [21]. Based on data from sites who have expressed interest in being involved in SPeEDy, 36% of operations to repair the rotator cuff are for traumatic tears which equates to 3 308 operations in the NHS in 2015/2016 with direct costs (surgery and post-operative physiotherapy) of £10 to £19.2 million. Two previous studies have evaluated the impact of physiotherapy on the need for surgery with one reporting that 75% of patients with non-traumatic tears of the rotator cuff did not subsequently require surgery [22]. A RCT evaluating the impact of physiotherapist-led exercise [23] on the need for subacromial decompression surgery reported that 80% of participants did not subsequently require surgery. Cautiously extrapolating this data, if an out-patient physiotherapist-led exercise programme resulted in 50% of patients not requiring surgery, for an outlay of £380 420 to £674 832 (3 308 x £115 to £204), there would be considerable NHS treatment cost savings per year of £4.8 to £9.3 million. If societal costs are added to this calculation, including work costs, this figure would rise considerably. This cost-saving is in the context of rising incidence of rotator cuff tears over time.

Hence, in relation to this common and burdensome problem there is considerable uncertainty and lack of evidence from RCTs to inform decision-making. Beyond the ACCURATE Trial (NCT02885714), a clinical trials registry search identified two further ongoing RCTs (NCT01498198; NCT02059473). The

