first of these is not restricted to traumatic rotator cuff tears, where most uncertainty exists, and the latter, in Sweden (n= 50), will not give answers to the feasibility of a future main RCT in the UK. Therefore, considering issues relating to cost, surgical risk (including infection and post-operative stiffness [24]) and patient and NHS burden associated with surgical intervention there is a strong ethical argument to urgently conduct high-quality research in this area. In a resource limited context, it is not acceptable to continue to provide invasive and expensive interventions without evidence of comparative effectiveness. Furthermore, the James Lind Alliance have identified this idea as a research priority in upper limb orthopaedic research [25].

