3.3 Outcome measures/endpoints

Feasibility outcomes:

- 1) Numbers of patients screened, number eligible, number approached, number consenting, number randomised, and number accepting allocation
- 2) Numbers of participants continuing in allocated treatment
- 3) Follow-up response rates to questionnaires at three and six months post-randomisation (including Oxford Shoulder Score and EQ-5D-5L)
- 4) Data from screening logs, including reasons for not approaching potentially eligible patients to inform determination of zone of clinical equipoise
- 5) Numbers of participants receiving treatment (surgery or PT-led exercise) other than that which was allocated to determine proportion of participants who cross-over
- 6) Feasibility of recruiting participating sites and numbers of additional sites who are interested in participating in the main trial
- 7) Participant satisfaction with the interventions on a five-point ordinal scale; Very Satisfied/Satisfied/Neutral/Dissatisfied/Very Dissatisfied
- 8) Barriers and facilitators to recruitment, retention and treatment cross-over (qualitative data; audio recording and individual interviews).

Clinical outcomes:

- 1) Pain and disability assessed using the Oxford Shoulder Score (OSS) at baseline, three and six months post-randomisation by post with telephone call for minimum data collection if no response to reminder postal questionnaire
- 2) Health related quality of life assessed using the EQ-5D-5L at baseline, three and six months post-randomisation by post with telephone call for minimum data collection if no response to reminder postal questionnaire
- 3) Days lost from work due to the shoulder problem at three and six months post-randomisation via postal questionnaire
- 4) Time taken to return to driving, if applicable, via questionnaire at three and six months post-randomisation via postal questionnaire
- 5) Number and type of adverse events for up to six months post-randomisation via patient self-report questionnaire or telephone Minimal Data Collection (MDC) at three and six months and via surgeon, physiotherapist or GP report.

Self-report data relating to further health care resource use, including NHS- and private borne service and medication costs will also be collected.

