7.2 Consent

Interested and eligible patients will be required to provide written informed consent before participating (see reference below to optional Quintet Recruitment Intervention (QRI) and optional six month qualitative interviews). Typically, written informed consent will be sought at the time of attendance at the orthopaedic clinic or other convenient time prior to the surgery if the patient requests more time to consider participation in the trial. A clinician or RHCP, who will have received appropriate training and is authorised on the trial delegation log, will obtain informed consent. A record of the consent process and a copy of the consent form will be kept in the patients' medical records. The original consent form will be retained in the Study Site File and a copy will be given to the participant. A copy will also be sent to Keele CTU for monitoring purposes. Participants in the SPeEDy RCT have the right to withdraw from treatment and/ or completion of outcome measures at any time without any consequence to any future care they receive. The GP of each trial participant will be sent a letter to confirm that their patient is taking part in the research study.

On receipt of written informed consent, the baseline questionnaire will be completed prior to randomisation. The participant will then access the interventions as per usual treatment pathways, including being placed

on a waiting list for surgery or physiotherapy. Time to intervention will be variable between treatment arms and between treatment sites and will be recorded and reported accordingly, including the proportion of participants who have not commenced their allocated treatment at the three and six month follow-up time points. Should this pilot and feasibility trial prove feasible, the statistical analysis plan for any future main trial will not control for this variation but it will be accounted for, as a co-variate. The current median wait for surgery in the NHS is 74 days and between 14 to 42 days for physiotherapy.

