7.8 Follow-up assessments

To meet the pre-specified objectives, the following data will be collected:

Measure	Description	3 months	3 months MDC	6 months	6 months MDC
Clinical status					
Shoulder Pain	Oxford Shoulder Score (OSS); 12 items, 5 discrete responses per item	✓	✓	✓	✓
Shoulder Function	Oxford Shoulder Score (OSS); 12 items, 5 discrete responses per item	✓	✓	✓	✓
Health related quality of life	EuroQol:EQ-5D-5L	✓	✓	✓	✓
Global change measure	Via questionnaire	✓	✓	✓	✓
Time taken to return to work (if applicable)	Via questionnaire	✓		✓	
Time taken to return to driving (if applicable)	Via questionnaire	✓		✓	
Adverse events	Via questionnaire and clinician report	✓	✓	✓	✓
Trial assessments/ Process Outcomes					
Patient participant satisfaction with the interventions	Participant satisfaction with intervention using a questionnaire with 5-point ordinal satisfaction question; very satisfied/satisfied/neutral/dissatisfied/very dissatisfied	✓		✓	
Health Care Utilisation					
Health Care Resource Use (including medication use)	Health Care Resource Use Questionnaire	✓		✓	
Days lost from work (if applicable)	Days lost from work due to the shoulder problem as a component question of Health Care Resource Use Questionnaire	✓		✓	
Date treatment commenced (surgery or physiotherapist-led exercise)	Via on-site Research Health Care Practitioner				

MDC = Minimum Data Collection over the telephone

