Once a SAE is identified and reported, this information will be passed to the Trial Manager who will ensure that the necessary paperwork is completed and inform the CI. In line with Keele University’s HSCR QMS SOPs the reporting clinician is to give their assessment and the CI will assess whether the event is related to or resulted from any of the trial procedures or interventions and expectedness, according to the process laid out in Keele University’s HSCR QMS SOPs. Any SAE considered to be related to the trial procedures and/ or unexpected will be reported to the Sponsor, REC and the TSC Chair by the CI within 15 days of becoming aware of the event. SAEs occurring later than six months post randomisation do not need reporting.

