10.5 Trial timeline

Month	1	2	3	4	5	6	7	8	9	10	11	12	13	14	15	16	17	18	19	20	21	22	23	24	25	26	27	28	29	30	31	32	33	34	35	36							
Protocol finalisation	█	█	█	█	█	█																																					
TMG meetings			█	█	█	█	█		█	█	█	█	█	█	█	█	█	█	█	█	█	█	█	█	█	█	█	█	█	█	█	█	█	█	█	█	█						
PPIE meetings	█				█												█																				█						
TSC meetings						█									█				█																			█					
Approvals					█	█	█	█	█	█	█	█	█																														
Site preparation									█	█	█	█																															
Recruitment (RCT)										█	█	█	█	█	█	█	█	█	█	█	█	█	█	█	█	█	█	█	█	█	█	█	█	█	█	█	█	█					
QRI										█	█	█	█	█	█	█	█	█	█	█	█	█	█	█	█	█	█	█	█	█	█	█	█	█	█	█	█	█					
Follow-up (RCT)													█	█	█	█	█	█	█	█	█	█	█	█	█	█	█	█	█	█	█	█	█	█	█	█	█	█					
Qualitative data collection & analysis																	█	█	█	█	█	█	█	█	█	█	█	█	█	█	█	█	█	█	█	█	█	█					
Data analysis (RCT)																																						█	█	█	█		
Study close down																																								█	█	█	█

TMG = Trial Management Group/ PPIE = Patient & Public Involvement & Engagement/ TSC = Trial Steering Committee/ QRI = Quintet Recruitment Intervention/ Follow-up (RCT) includes time lag to intervention

Months 1 to 9: Study set-up period including Health Research Authority approval, commencement of site initiation and trial-specific training. Initial TSC meeting.

Months 10 to 12: Complete site set-up and commence participant recruitment (15 months' recruitment in total), and commence QRI.

Months 13 to 24: Commence outcome data collection, including qualitative interviews, complete QRI and make recommendations to TMG, and complete recruitment for RCT.

Months 25 to 32: Complete outcome data collection and initiate data analysis.

Months 33 to 36: Final PPIE group and TSC meetings with assessment of RCT success according to agreed criteria.

Months 37 to 48 (beyond study period but within fellowship period of CI): Final report writing, main trial application if applicable, initiate dissemination plan and archiving.

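### Adverse event capture closes six months after randomisation, which leaves less observation after surgery than after exercise starts, and the Study Summary states a different clock

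*Combined protocol and SAP*

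**What the plan says.** Section 3.3, clinical outcome 5, defines the outcome as "Number and type of adverse events for up to six months post-randomisation", gathered by questionnaire, telephone minimum data collection and clinician or GP report. Section 10.4 closes with "SAEs occurring later than six months post randomisation do not need reporting". Neither section allows for when treatment begins.

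Section 7.2 gives the expected delays: "The current median wait for surgery in the NHS is 74 days and between 14 to 42 days for physiotherapy". It also promises to record and report time to treatment, and the proportion not yet started at three and six months. Section 7.8 lists the treatment start date among the data collected.

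Other places point to a different clock. The Study Summary, under objective 8, times the self-report adverse event questionnaires at three and six months after surgery. The footnote to the timeline in section 10.5 says "Follow-up (RCT) includes time lag to intervention". Section 10.4 also asks clinicians for events they learn of while the trial is running, and section 7.11 ends the trial only when data collection is complete.

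The Background names infection and stiffness as surgical risks. Section 10.4 lists two expected SAEs: a repair that re-ruptures or does not heal, and repair surgery in a participant allocated to exercise.

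**The concern.** Objective 8 is to establish how many adverse events occur and of what kind. There is no data monitoring committee, so under section 10.1.1 the Trial Steering Committee alone reviews safety and advises on progression.

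Complications of an operation cannot precede it. A window that starts at randomisation and ignores the wait therefore spends part of its length on time when the surgery arm cannot yet have them. The exercise arm loses less of the window because its wait is shorter. Crude counts would then set unequal post-treatment time side by side, and events after the cut-off need never reach the sponsor, the ethics committee or the committee chair.

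Cross-over repairs sharpen the point. Progression criterion iii in section 8.3 accepts cross-over below 25% at six months, which is up to 9 of 38 exercise participants (9/38 = 23.7%). Surgery after exercise is thus an expected part of the pathway, and those operations come latest in the window.

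Separately, a site that reads the Study Summary and a site that reads section 10.4 could apply different end dates.

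**Working it through.** The protocol gives no figure for observation time after treatment, so there is none to reproduce.

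**Inputs**
- Window: six months from randomisation (3.3, 10.4), taken as 365.25/2 = 182.6 days; 180 to 184 days is used as a check.
- Waits: 74 days (median) for surgery; 14 to 42 days for physiotherapy (7.2).
- Exercise programme: 12 weeks = 84 days (4.1).
- Recruitment in months 10 to 24; outcome data collection complete by month 32 (10.5).

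**1. Allocated treatment.** Post-treatment observation = window − wait.
- Surgery at the median wait: 182.6 − 74 = 108.6 days.
- Exercise: 182.6 − 42 = 140.6 days to 182.6 − 14 = 168.6 days.
- Shortfall for surgery: 140.6 − 108.6 = 32 days to 168.6 − 108.6 = 60 days.
- Ratio: 108.6/168.6 = 0.64 to 108.6/140.6 = 0.77.
- With a 180-day or 184-day window, surgery has 106 or 110 days, and the ratios move by less than one percentage point.

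**2. Three-month questionnaire.** 182.6/2 − 74 = 17.3 days after an operation at the median wait.

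**3. Cross-over repair.** Day of surgery = physiotherapy wait + time in programme + new surgical wait. Assumption: a fresh 74-day wait applies. The protocol states neither that wait nor when a request may be made.

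| Repair requested | Day of surgery | Days left in window |
|---|---|---|
| At randomisation | 74 | 109 |
| First exercise session | 14+74 = 88 to 42+74 = 116 | 95 to 67 |
| Six weeks into programme | 14+42+74 = 130 to 42+42+74 = 158 | 53 to 25 |
| After all 12 weeks | 14+84+74 = 172 to 42+84+74 = 200 | 11 left to 17 past the end |

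**4. Room in the timeline** (30.4 days per month).
- Last recruit under a strict six-month clock: 24 + 6 = month 30, two months before month 32.
- Last recruit followed for six months after a median-wait operation: 24 + 74/30.4 + 6 = month 32.4.
- Cross-over repair at day 172 to 200 followed for six months: (172 + 182.6)/30.4 = 11.7 to (200 + 182.6)/30.4 = 12.6 months after randomisation. Full follow-up by month 32 then requires randomisation by about month 19 to 20 (32 − 12.6 = 19.4; 32 − 11.7 = 20.3).

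**The case against.** By allocated arm, both groups are watched for the same six months from randomisation, which is a legitimate clock for comparing two pathways that include their waits. The trial is a pilot centred on process outcomes, it plans no formal safety comparison, and none of the four criteria in section 8.3 concerns adverse events. Waits are openly acknowledged, and start dates are recorded, so rates per unit of post-treatment time could be calculated. The 74 days is a general NHS median, not a figure measured at the trial sites. The protocol does not say when infection, stiffness or re-rupture would appear, so the number of events missed is unknown. A cross-over operation is itself a reportable SAE if it takes place within six months.

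Most of this stands, and it limits how serious the point is. It does not remove it: a start date supplies a denominator but cannot recover an event that nobody was asked to report.

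Extending follow-up only for operated participants would also reverse the imbalance. At least 183 days after surgery would then face 141 to 169 days after exercise starts, so any change must apply the same rule in both arms.

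**Conclusion.** The point holds in a limited form. Sections 3.3 and 10.4 end capture six months after randomisation, and the Study Summary and the section 10.5 footnote do not agree with them. At the waits the protocol quotes, surgery has about 109 days of post-treatment observation against 141 to 169 for exercise. That result rests on the NHS waits applying at the trial sites. The cross-over figures rest further on a new 74-day wait and an assumed request time. The amendment is worth making, but the problem does not undermine the pilot.

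Four stronger readings are tempting, and the documents do not support them.
- A reader might infer that every reporting route runs from randomisation. The Study Summary says otherwise for the questionnaires.
- A reader might infer that complications of cross-over repairs fall almost wholly outside the window. That is only the last row of the table; requests up to six weeks into the programme leave about 25 to 109 days.
- A reader might infer that the window closes before the shortest recovery described. The Background has a sling for at most six weeks, "followed by an exercise programme to regain movement, strength and function over a three to six-month period". Adding the sling maximum to the rehabilitation minimum gives 42 + 91.3 = 133.3 days, but that is not the shortest course: three months alone is 91.3 days, inside the 109. Nor is rehabilitation time a stated period of risk.
- A reader might put numbers out of 38 on participants with little or no post-operative observation. The protocol gives a median and no spread. Under assumed log-normal waits (log-SD 0.3 to 1.0) or exponential waits, the share not operated on by six months runs from 0.1% to 18%, too wide to use.

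**What to change.** 1. Put the Study Summary (objective 8), section 3.3, section 10.4 and the section 10.5 footnote on one stated clock. A clock that starts at surgery is undefined for exercise participants who never have an operation.
2. Replace the last sentence of section 10.4, and match section 3.3 clinical outcome 5, along these lines: in both arms, clinician-reported adverse events and SAEs are collected until six months after randomisation or six months after the start of trial treatment (including any cross-over repair), whichever is later, with a cut-off at the end of outcome data collection in month 32. Complete this from the case-note review already planned in section 4.1. The GP letter should carry the same end date.
3. Leave the OSS, the EQ-5D-5L and the questionnaire time points as they are.
4. Beside counts by allocated arm, report adverse events by treatment received per person-month since treatment start, with person-time divided at any cross-over repair. This needs the start dates already collected plus the date of each such repair.

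At the quoted waits, capture would run to day 74 + 182.6 = 257 for surgery at the median and to day 197 to 225 for exercise (14 + 182.6 to 42 + 182.6), giving equal post-treatment time.

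The cost is an amendment, a later case-note check and one more table. Self-report still stops at the six-month questionnaire. Late recruits, and late cross-over repairs above all, remain truncated at month 32, and the report should say so.

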10.5 Trial timeline

Month	1	2	3	4	5	6	7	8	9	10	11	12	13	14	15	16	17	18	19	20	21	22	23	24	25	26	27	28	29	30	31	32	33	34	35	36							
Protocol finalisation	█	█	█	█	█	█																																					
TMG meetings			█	█	█	█	█		█	█	█	█	█	█	█	█	█	█	█	█	█	█	█	█	█	█	█	█	█	█	█	█	█	█	█	█	█						
PPIE meetings	█				█												█																				█						
TSC meetings						█									█				█																			█					
Approvals					█	█	█	█	█	█	█	█	█																														
Site preparation									█	█	█	█																															
Recruitment (RCT)										█	█	█	█	█	█	█	█	█	█	█	█	█	█	█	█	█	█	█	█	█	█	█	█	█	█	█	█	█					
QRI										█	█	█	█	█	█	█	█	█	█	█	█	█	█	█	█	█	█	█	█	█	█	█	█	█	█	█	█	█					
Follow-up (RCT)													█	█	█	█	█	█	█	█	█	█	█	█	█	█	█	█	█	█	█	█	█	█	█	█	█	█					
Qualitative data collection & analysis																	█	█	█	█	█	█	█	█	█	█	█	█	█	█	█	█	█	█	█	█	█	█					
Data analysis (RCT)																																						█	█	█	█		
Study close down																																								█	█	█	█

TMG = Trial Management Group/ PPIE = Patient & Public Involvement & Engagement/ TSC = Trial Steering Committee/ QRI = Quintet Recruitment Intervention/ Follow-up (RCT) includes time lag to intervention

Months 1 to 9: Study set-up period including Health Research Authority approval, commencement of site initiation and trial-specific training. Initial TSC meeting.

Months 10 to 12: Complete site set-up and commence participant recruitment (15 months' recruitment in total), and commence QRI.

Months 13 to 24: Commence outcome data collection, including qualitative interviews, complete QRI and make recommendations to TMG, and complete recruitment for RCT.

Months 25 to 32: Complete outcome data collection and initiate data analysis.

Months 33 to 36: Final PPIE group and TSC meetings with assessment of RCT success according to agreed criteria.

Months 37 to 48 (beyond study period but within fellowship period of CI): Final report writing, main trial application if applicable, initiate dissemination plan and archiving.

11 ETHICAL AND REGULATORY CONSIDERATIONS

11.1 Research Ethics Committee (REC) review & reports

The study will be submitted to and approved by the HRA (which includes REC) to gain the appropriate NHS Permissions prior to recruiting participants into the study. Keele CTU will provide the final protocol, participant information sheets, consent forms and all other relevant study documentation as part of the ethical approval process.

Following initial approval from the REC, they will continually be informed of all substantial changes to the management of trial. Routine reporting will take place in line with REC requirements.

All correspondence with the REC will be retained in the Trial Master File (TMF). Study Site Files including details of the original REC approval will be updated with any REC approval letters acknowledging a substantial change.

11.2 Peer review

This trial has been subject to internal peer review, and external peer review by the funding body (NIHR Post-Doctoral Fellowship scheme).

